2.0 Data Analysis Considerations

2.1 Types of Analyses

Analyses will consist of summarizing efficacy and safety data. Unless otherwise stated, two-sided P values <0.05 will be considered as statistically significant.

The following standards will be applied for the analyses unless otherwise specified. Simple summary statistics (descriptive statistics) for continuous data are: n (number of non-missing observations), mean, median, standard deviation, minimum, and maximum. The frequency count and percentage will be used to summarize categorical data. Summary statistics will be presented by treatment. All data collected will be presented in the by-subject data listings, sorted by subject and by time point, where appropriate.

Additionally, the randomization is stratified by high and low dose of the investigational product. Therefore, descriptive statistics, grouped by both

treatment and dose level strata, will be presented using the same descriptive analyses described above for continuous and categorical data, as applicable.

2.2 Analysis Populations

The following analysis populations will be defined:

Safety: This population consists of all randomized subjects who receive at least 1 dose of IP (amifampridine or placebo).

Full Analysis Set (FAS), Intent to Treat Population: This population consists of all randomized subjects who receive at least 1 dose of IP (amifampridine or placebo) and have at least one post-treatment efficacy assessment.

Per Protocol (PP): This population is a subset of the FAS population, excluding subjects with major protocol deviations. The PP population will include all subjects who:

- Have no major protocol deviations or inclusion/exclusion criteria deviations that might potentially affect efficacy, and
- Subjects who took at least 80% of the required treatment doses and remained enrolled for at least 4 days.

Evaluations obtained at the time of discontinuation will be included in the FAS and PP analyses, as applicable. Subjects who discontinue with no post-randomization data (no Day 0 and no Day 4 data) will be excluded from all efficacy analyses but will be included in the safety analyses.

Exclusion from the FAS and PP Populations will be finalized prior to database lock and subsequent unblinding.

2.2.1 Subgroup Definitions

Descriptive statistics for each efficacy variable will be provided by low dose (less than 60 mg/day) and high dose (60 mg/day, and higher) subgroups for subjects receiving amifampridine or placebo. No hypotheses will be tested in these subgroup analyses. See Section 7.0 for a list of tables presenting results by dose group.

2.3 Missing Data Conventions

No missing value imputation will be used in this analysis. All analyses will be based on the observed data. For subjects that discontinue prior to Day 4 due to treatment related disability ("Rescue"), the observations collected at the time of rescue will be analyzed with the other Day 4 observations.

2.4 Interim Analyses

There are no interim analyses planned for this study.

2.5 Study Center Considerations in the Data Analysis

A study center is defined as a treatment administration site or group of treatment administration sites under the control and supervision of the same Principal Investigator (PI).

There will be no selective pooling of study centers in the analysis. All calculations will be made on the combined results of all centers.

2.6 Documentation and Other Considerations

The data analyses will be conducted using SAS® Software, version 9.4 or later.

3.0 Analysis of Baseline Subject Characteristics

Baseline and demographic characteristics will be summarized by treatment and overall for all subjects in the safety population. Age and baseline weight will be displayed via summary statistics (mean, median, sample size, standard deviation, minimum, and maximum). Gender and ethnicity will be summarized via counts and percentages.

A detailed listing of demographics data for each subject will also be provided as shown in Appendix B.

4.0 Analysis of Efficacy

4.1 Description of Efficacy Variables

4.1.1 Primary Efficacy Variables

The co-primary efficacy variables for the study are the following:

- Subject Global Impression (SGI) score
- Quantitative Myasthenia Gravis (QMG) score

The calculations and analyses pertaining to each of the above variables are shown in Section 4.2.1.

4.1.2 Secondary and Exploratory Efficacy Variables

The secondary and exploratory efficacy variables are the following:

- Clinical Global Impression of Improvement (CGI-I) score (secondary)
- Triple Timed Up and Go (3TUG) result (exploratory)
- Subject most bothersome symptom question (exploratory)
- QMG limb domains (exploratory)

The calculations and analyses pertaining to each of the above variables are shown in Section 4.2.2.

4.2 Analysis of Efficacy Variables

4.2.1 Primary Efficacy Analysis

Primary efficacy analyses will be conducted on the FAS and PP populations, with the FAS population serving as the primary analysis set. For both primary efficacy variables, change from baseline (CFB) will be computed as the post-treatment result (Day 4) minus the Baseline result (Day 0). The post-treatment result will be the result obtained on Day 4, unless the subject discontinued treatment early, in which case the post-treatment result may be obtained at an earlier time point.

Summary statistics for the QMG Day 0 assessment, QMG Day 4 assessment, and the corresponding CFB will be presented by treatment. The analysis of CFB for Total QMG Score is a co-primary efficacy endpoint and analysis will be performed by fitting a fixed effects linear model to the data with CFB as the response. The model will include terms for treatment and QMG at Baseline. The following test comparing the least squares (LS) means will be conducted to evaluate the treatment effect:

H_{A,0}: LSMeanQMG(A) = LSMeanQMG(P) vs. H_{A,1}: LSMeanQMG(A) \neq LSMeanQMG(P),

where LSMeanQMG(A) is the QMG LS mean of the amifampridine treatment group and LSMeanQMG(P) is the QMG LS mean of the placebo treatment group.

The raw individual QMG scores (each individual QMG domain) for Day 0, Day 4, and CFB will be summarized by treatment and dose within treatment. Additional between-treatment comparisons for several of the individual QMG domains, and the sum of these domains, will be performed using a fixed effects linear model as an exploratory endpoint. No inferential procedures will be performed on the other QMG domains. See section 4.2.2 for details.

Summary statistics for SGI score and the corresponding CFB will be presented by treatment. The analysis of CFB for SGI is a co-primary efficacy endpoint and analysis will be performed by fitting a fixed effects linear model to the data with CFB as the response. The model will include terms for treatment and SGI at Baseline. The following test comparing the LS means will be conducted to evaluate the treatment effect:

 $H_{B,0}$: LSMeanSGI(A) = LSMeanSGI(P) vs. $H_{B,1}$: LSMeanSGI(A) \neq LSMeanSGI(P),

where LSMeanSGI(A) is the SGI LS mean of the amifampridine treatment group and LSMeanSGI(P) is the SGI LS mean of the placebo treatment group.

A sensitivity analysis of the co-primary endpoints will be conducted to evaluate the patterns of early treatment discontinuation. For each co-primary endpoint, a randomization test will be conducted to determine if the results from the primary analysis are supported. The randomization test is an alternative to a full permutation, and will evaluate the fixed effects model specified above using permutations of the treatment group assignments. If early discontinuations are not associated with treatment, then it is expected that the p-value resulting from the randomization test will yield the same statistical interpretation as the p-value resulting from the primary analysis.

A data listing of the primary efficacy data will be constructed as shown in Appendix B.

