11.4 Early Discontinuation Visit

Any patient that discontinues from the study, regardless of the reason, will be requested to complete all Early Discontinuation visit assessments/procedures as listed below after the last dose of study medication. Every reasonable effort should be made to contact any patient who is lost to follow-up.

In cases of Early Discontinuation, medication will have been stopped some time prior to seeing the patient for the below assessments. The date and time of the last dose of medication should be recorded in relation to when the assessments are performed.

- Assessment of AEs/SAEs
- Vital signs
- Concomitant medications
- IP accountability
- SGI
- CGI-I (compared to Day 0)
- Patient most bothersome symptom, Question 2
- QMG
- 3TUG

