A sensitivity analysis of the coprimary endpoints will be conducted to evaluate the patterns of early treatment discontinuation. For each coprimary endpoint, a randomization test will be conducted to determine if the results from the primary analysis are supported. The randomization test is an alternative to a full permutation, and will evaluate the fixed effects model specified above using permutations of the treatment group assignments. If early discontinuations are not associated with treatment, then it is expected that the p-value resulting from the randomization test will yield the same statistical interpretation as the p-value resulting from the primary analysis.

The proportion of patients with at least 20% increase in average time for 3TUG will be summarized by treatment and analyzed using Fisher's Exact Test. The assessment of the Patient's Most Bothersome Symptom will be summarized by treatment and analyzed using a Wilcoxon Rank Sum Test.

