		Post-Baseline	RAW	XXX	XXX	XXX	XXX	XXX	XXX
			CFB	XXX	XXX	XXX	XXX	XXX	XXX
	High Dose (> 60mg/day)	Day O (Baseline)	RAW	XXX	XXX	XXX	XXX	XXX	XXX
		Post-Baseline	RAW	XXX	XXX	XXX	XXX	XXX	XXX
			CFB	XXX	XXX	XXX	XXX	XXX	XXX
	All Doses	Day O (Baseline)	RAW	XXX	XXX	XXX	XXX	XXX	XXX
		Post-Baseline	RAW	XXX	XXX	XXX	XXX	XXX	XXX
			CFB	XXX	XXX	XXX	XXX	XXX	XXX

^a The post-treatment result will be the result obtained on Day 4, unless the subject discontinued treatment early, in which case the post-treatment result may be obtained at an earlier time point.

 $^{\rm b}$ RAW = observed data entered in the database; CFB = change from baseline.

Table Creation Date: (DD-MMM-YYYY)

Source Program: xxxxxx.sas Source Listing: Data Listing 13

Table 21. SGI Score CFB Analysis Catalyst Pharmaceuticals, Inc. - LMS-003 FAS Population (N=xxx)

Statistic ^a	Amifampridine	Placebo
n	XXX	XXX
Least Squares (LS) Mean of Change from Baseline (CFB)	XXX	XXX
Between-Treatment Difference in LS Means	XXX	
95% CI for Between-Treatment Difference in LS Means	(xxx, xxx)	
P-value for Between-Treatment Difference in LS Means	XXX	

^a CFB for SGI score was modeled as the response, with fixed effects terms for treatment and QMG at Baseline. Table Creation Date: (DD-MMM-YYYY) Source Program: xxxxxx.sas Source Listing: Data Listing 13

Table 23. QMG Total Score and SGI Score Sensitivity Analysis Catalyst Pharmaceuticals, Inc. - LMS-003 FAS Population (N=xxx)

Statistic ^a	QMG Total Score	SGI Score
P-value for Between-Treatment Difference in LS Means	XXX	XXX

^a P-value based on conducting a randomization test by running the fixed effects linear model analysis on permuted treatment assignments. For each of the xxxx permutations, CFB was modeled as the response for each endpoint, with fixed effects terms for treatment and score at Baseline. Table Creation Date: (DD-MMM-YYY) Source Program: xxxxxxx.sas Source Listing: Data Listing 13, Data Listing 14

Table format will be repeated for the PP Population.

STATKING Clinical Services Version 1.0

Page 35 of 71

Page	x	of	v
ruge		 	y

Table 25.	CGI-I Scores Summary Statistics
Catalyst	Pharmaceuticals, Inc LMS-003
	FAS Population (N=xxx)

			Std					
Treatment	Time Point	Mean	Dev	n	Min	Max	Median	P-value ^a
Amifampridine	Day 4	XXX	XXX	XXX	XXX	XXX	XXX	XXX
Placebo	Day 4	XXX	XXX	XXX	XXX	XXX	xxx	

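### The randomization test in SAP 4.2.1 uses no discontinuation information, so its agreement with the primary p-value says nothing about early discontinuation

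*SAP*

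**What the plan says.** **Pooling of early scores.** For patients rescued before Day 4, SAP 2.3 states that "the observations collected at the time of rescue will be analyzed with the other Day 4 observations", and it allows no imputation. SAP 4.2.1 likewise uses an earlier post-treatment result when a patient stops early.

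**Primary model.** For each co-primary endpoint, change from baseline is modelled on treatment and the baseline score (SAP 4.2.1).

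**Sensitivity analysis.** One is planned for the co-primary endpoints. Its purpose in the SAP is: "A sensitivity analysis of the co-primary endpoints will be conducted to evaluate the patterns of early treatment discontinuation". Protocol 13.4 has the same sentence: "A sensitivity analysis of the coprimary endpoints will be conducted to evaluate the patterns of early treatment discontinuation". The method is a randomization test. The rule for reading it begins: "If early discontinuations are not associated with treatment, then it is expected that the p-value resulting from the randomization test will yield the same". In other words, the SAP expects the two p-values to lead to one conclusion when discontinuation is unrelated to treatment.

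**What is computed.** The Table 23 footnote in SAP Appendix B describes a "randomization test by running the fixed effects linear model analysis on permuted treatment assignments", "with fixed effects terms for treatment and score at Baseline". The output is one p-value per endpoint.

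**Nearest alternative.** The co-primary models are repeated in the per-protocol (PP) set, which requires: "Subjects who took at least 80% of the required treatment doses and remained enrolled for at least 4 days".

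**How early scores arise.** Protocol 8.2.3 allows a patient whose LEMS worsens to go onto open-label drug, with early-discontinuation assessments done as for Day 4. Protocol 11.4 adds: "In cases of Early Discontinuation, medication will have been stopped some time prior to seeing the patient for the below assessments". Scheduled Day 4 efficacy assessments start 40 minutes after a dose given in clinic (Protocol 8.3.3).

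**The concern.** A sensitivity analysis for early discontinuation should change something about how the early observations are handled and show whether the result moves. This one changes only the reference distribution for the test statistic. That is a reasonable check with about 26 patients, but it answers a different question.

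The risk lies in the reporting. Under the SAP's rule, two matching p-values would be presented as reassurance that discontinuation is unrelated to treatment. If they match almost always, whatever the pattern of discontinuation, that reassurance is empty. This is a drug-withdrawal design in which worsening LEMS is a named reason for rescue, so more rescues on placebo are foreseeable. Early scores enter both co-primary endpoints, and nothing in the plan shows how far either result depends on their values.

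**Working it through.** The plan gives no figure on this point to reproduce. The central step is logical; the simulation only illustrates it.

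**Step 1. Inputs of the two tests.** The primary model is

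CFB_i = μ + τ·treatment_i + β·baseline_i + ε_i,

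with p from the t statistic for τ. The randomization test keeps every CFB and baseline value, permutes the treatment labels B times, refits, and takes

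p = (1 + number of permutations with |t_b| ≥ |t_observed|) / (B + 1).

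(The t statistic is my choice; the SAP does not name one.) Neither formula contains a rescue flag, a date of last dose or a treatment duration. For a given data set, the randomization p-value is the same whichever patients are marked as early leavers. This needs no assumption about rescue rates.

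**Step 2. How often the two decisions agree, QMG scale.** From SAP 1.3: difference 3.5, SD 3, two-sided 0.05, 26 patients, hence 13 per arm. Assumed, because the documents are silent: the share rescued, and rescue scores either 4 points worse or taken after an open-label restart that restores the drug effect. There were 999 permutations and 1,000 trials per scenario. The Monte Carlo standard error of agreement is about √(0.98 × 0.02 / 1,000) = 0.4 points.

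| True difference | Rescued, placebo / drug | Rescue scores | Mean estimate | Primary p<0.05 | Randomization p<0.05 | Same decision |
|---|---|---|---|---|---|---|
| 0 | none | – | -0.01 | 3.9% | 4.0% | 99.7% |
| 0 | 30% / 0% | 4 worse | 1.23 | 14.9% | 14.1% | 98.6% |
| 0 | 50% / 0% | 4 worse | 1.93 | 27.7% | 27.2% | 98.1% |
| 3.5 | none | – | 3.58 | 81.1% | 79.9% | 98.2% |
| 3.5 | 20% / 20% | 4 worse | 3.42 | 67.1% | 67.1% | 98.0% |
| 3.5 | 30% / 0% | after restart | 2.45 | 46.1% | 45.5% | 97.8% |
| 3.5 | 50% / 0% | after restart | 1.78 | 27.2% | 26.4% | 98.2% |

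Over all 19 scenarios run, agreement was 97.7% to 99.8%, and the median absolute gap between the two p-values was 0.001 to 0.008. Where the assumed rescue scores push the estimate up or down, the randomization test moves with the primary test. It reproduces the distortion and cannot reveal it.

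**Step 3. Both endpoints, bounded integer scores.** 13 per arm; QMG baseline N(8, 3) (assumed), limits 0-39 from the 13 items scored 0-3 in Protocol Appendix 1; SGI baseline N(5.9, 1.2) from Protocol 6.4.2, change difference 2.1 and SD 2 from SAP 1.3, limits 1-7. There were 2,000 permutations and 3,000 trials per scenario, with a standard error of about 0.2 points. Rescue scores were made 2 points (QMG) or 1 point (SGI) worse.

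| Agreement at 0.05 | No rescue | 3 per arm at random, distorted | 5 worst placebo only, distorted |
|---|---|---|---|
| QMG | 98.8% | 98.6% | 99.0% |
| SGI | 98.4% | 98.1% | 98.5% |

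The SAP's rule compares rescue unrelated to treatment (middle column) with rescue related to it (right column). The ratio of the chances of agreement is 0.9897 / 0.9863 = 1.003 for QMG and 0.9847 / 0.981 = 1.004 for SGI. A ratio of 1 means that agreement carries no information.

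**Step 4. Do other outputs fill the gap?** Table 1 counts withdrawals and reasons by arm; Data Listing 1 gives date and reason; Listings 12, 13 and 17 give scores. These describe. Tables 14 and 22 repeat the models in PP, which may drop early leavers, but that deletes patients on a post-randomization event linked to outcome. Alternative denominators exist only for exploratory 3TUG (SAP 4.2.2). None assigns early scores another value.

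**The case against.** **It is one mislabelled supportive analysis.** True. The primary analysis does not depend on it, and rewording alone removes the false inference.

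**The different-conditions argument is weaker than it looks.** A placebo patient's Day 4 dose is placebo, so being assessed off medication has no pharmacological meaning in that arm. On drug, with a half-life of 1.8 hours (Protocol 6.4.1), assessment after stopping would worsen scores and count against the drug. Protocol 11.4 also requires the time of the last dose to be recorded. This stands. What remains open is whether scoring precedes an open-label restart, which Protocol 8.2.3 does not say, and the SGI's 3-day recall (Appendix 2), which for a rescue on Day 1 or 2 reaches back before randomization. The direction of any effect is not fixed.

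**A tipping-point analysis can overturn real effects.** Also true. With the worst 1, 2 or 5 of 13 placebo patients rescued and their scores undistorted (an assumed scenario), a shift capped at the drug-arm mean removed significance in 16.1%, 33.4% and 87.4% of significant QMG trials. Dropping those patients did so in 11.7%, 23.1% and 65.9%. For SGI the figures were 22.5%, 42.4% and 90.4% against 15.9%, 31.3% and 74.1%. Nor does it detect bias reliably: in a separate QMG run with a true 3.5-point effect, it tipped in 15.7%, 33.0% and 86.7% of trials with undistorted scores and in 16.2%, 34.8% and 88.0% with scores 2 points too bad. It measures dependence on the early scores, not their error, and is one option among several.

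**Existing outputs already inform.** In part. With about 26 patients, a reader can follow each early leaver through the listings. The PP set may even keep some: SAP 2.2 includes discontinuation evaluations as applicable, and a patient rescued on Day 3 might count as enrolled for four days (Days 0-3).

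**Conclusion.** The point holds. The randomization test cannot evaluate early discontinuation, and the SAP's reading rule is wrong as written rather than short of detail. That conclusion rests on the test's inputs alone. The 98-99% agreement illustrates it and depends on assumed rescue rates and score distortions.

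Two stronger readings are tempting, and the documents support neither. A reader might infer that the pooled rescue scores bias the co-primary results, or that significance would be lost if they were handled differently. The documents give no rescue rate and no size or direction for any distortion, so the rejection rates in the simulation and the loss-of-significance percentages belong to invented scenarios and are not expectations for this trial. A reader might also infer that the plan says nothing about discontinuation. It does, through Table 1, the listings and the PP repeats; what it lacks is an analysis that varies the early scores. The mislabelling leaves the primary estimate, test and error rate unchanged.

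**What to change.** In SAP 4.2.1, before unblinding:

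1. Keep the randomization test as a small-sample check of the primary p-value. Delete the words giving its purpose as evaluating discontinuation, and delete the final sentence that links agreement to discontinuation. Make the same edit in Protocol 13.4, or record the departure in the SAP.
2. Report by arm the number of rescue scores and of other early scores used in the FAS. As a supportive, descriptive analysis, refit each co-primary FAS model with those scores varied. One prespecified option is a tipping-point shift: move early change scores in 1-point steps toward the other arm's mean, stop at that mean and at the scale limits, and report the first shift with p ≥ 0.05, or that none was reached.
3. State beside that table that a low tipping point does not by itself show that the early scores are biased.

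No change to the rescue rules or the primary analysis is needed. The cost is some edited text and one short table, with no extra patients, visits or procedures. If rescues are few, the table will be nearly empty.

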4.2.2 Secondary and Exploratory Efficacy Analyses

Secondary and exploratory efficacy analyses will be conducted on the FAS and PP populations, with the FAS population serving as the primary analysis set.

Clinical Global Impression of Improvement (CGI-I)

CGI-I scores will be summarized by treatment group using descriptive statistics. A Wilcoxon Rank Sum Test will be conducted to assess for treatment group differences.

Triple Timed Up and Go (3TUG)

The number and proportion of subjects with at least a 20% increase in average time for 3TUG (i.e., a success) at Day 4 relative to Day 0 will be presented by treatment. For those subjects that are unable to complete the Day 4 assessment due to disability related to their disease, a success will be assigned to the subject by the site at the time of testing. The proportion will be computed in two ways: 1) using all subjects in the analysis population with Day 0 data as the denominator, regardless of whether or not they completed the Day 4 assessment; and 2) using only those subjects in the analysis population who completed both the Day 0 and Day 4 assessments. For each approach in calculating the proportion, a two-sided Fisher's Exact Test will be conducted to

test for a significant difference in the success proportions between treatment groups.

Patient Most Bothersome Symptom Question

For the Patient Most Bothersome Symptom (PMBS) question, change from baseline (CFB) will be computed as the post-treatment response (Day 4) minus the Baseline response (Day 0). The post-treatment response will be the result obtained on Day 4, unless the subject discontinued treatment early, in which case the post-treatment response may be obtained at an earlier time point.

Summary statistics for the PMBS Day 0 response, PBMS Day 4 response, and the corresponding CFB will be presented by treatment. The analysis of CFB for PMBS Score will be performed using Wilcoxon's Rank Sum Test.

QMG Limb Domains

Descriptive statistics for Day 0, Day 4, and CFB for the sum of the QMG scores for Right arm outstretched, Left arm outstretched, Right leg outstretched, and Left leg outstretched will be presented by treatment. As was described in section 4.2.1, summary statistics will be presented for each of these for individual domains. The CFB for each of these four individual domains, and for the sum of these four domains, will be performed by fitting a fixed effects linear model to the data with CFB as the response. The model will include terms for treatment and QMG score of the respective individual domain, or sum of these four domains, as applicable, at Baseline. The following test comparing the least squares (LS) means will be conducted to evaluate the treatment effect:

 $\begin{array}{l} H_{C,0} : LSMeanQMG(A) = LSMeanQMG(P) \\ & VS. \\ H_{C,1} : LSMeanQMG(A) \neq LSMeanQMG(P), \end{array}$

where LSMeanQMG(A) is the QMG LS mean of the amifampridine treatment group and LSMeanQMG(P) is the QMG LS mean of the placebo treatment group for each individual QMG domain described above, or sum of these 4 domains. A sensitivity analysis by a randomization test for the QMG limb domain analyses is not required.

All secondary and exploratory efficacy data will be listed as shown in Appendix B.

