^a P-value based on the Wilcoxon Rank Sum Test for treatment differences. Table Creation Date: (DD-MMM-YYYY) Source Program: xxxxxx.sas Source Listing: Data Listing 15

Treatment	Dose Group	Time Point	Data Type	Mean	Std Dev	n	Min	Max	Median
Amifampridine	Dose Group	IIME IOINC	Data Type	Mean	Dev	11	PILII	Max	Meditan
mariampridine	Loui Doco (< 60mg/dour)	Davi 4	RAW						
	Low Dose (< 60mg/day)	Day 4		XXX	XXX	XXX	XXX	XXX	XXX
	High Dose (> 60mg/day)	Day 4	RAW	XXX	XXX	XXX	XXX	XXX	XXX
	All Doses	Day 4	RAW	XXX	XXX	XXX	XXX	XXX	XXX
Placebo		-							
	Low Dose (< 60mg/day)	Day 4	RAW	XXX	XXX	XXX	XXX	XXX	XXX
	High Dose (> 60mg/day)	Day 4	RAW	XXX	XXX	XXX	XXX	XXX	XXX
	All Doses	Day 4	RAW	XXX	XXX	XXX	XXX	XXX	XXX

Table 27. CGI-I Scores Summary Statistics by Dose Group Catalyst Pharmaceuticals, Inc. - LMS-003 FAS Population (N=xxx)

Table Creation Date: (DD-MMM-YYYY) Source Program: xxxxxx.sas Source Listing: Data Listing 15

Table 29. Number and Proportion of Subjects with ≥ 20% Increase in 3TUG Average Time Catalyst Pharmaceuticals, Inc. - LMS-003 FAS Population (N=xxx)

Calculation	Amifampridine (N=xxx)	Placebo (N=xxx)	P-value ^a
Denominator Based on Subjects Who Completed Day 0 3TUG	xxx/xxx (xxx)	xxx/xxx (xxx)	XXX
Denominator Based on Subjects Who Completed Day 0 and Day 4 $3 extsf{TUG}$	xxx/xxx (xxx)	xxx/xxx (xxx)	XXX

^a P-value based on a two-sided Fisher's Exact Test of difference in treatment proportions. Table Creation Date: (DD-MMM-YYYY) Source Program: xxxxxx.sas Source Listing: Data Listing 16

Table format will be repeated for the PP Population.

STATKING Clinical Services Version 1.0

Page 38 of 71

Table 31. Number and Proportion of Subjects with \geq 20% Increase in 3TUG Average Time by Dose Group Catalyst Pharmaceuticals, Inc. - LMS-003 FAS Population (N=xxx)

Low Dose(< 60mg/day)

High Dose(\geq 60mg/day)

Calculation	Amifampridine (N=xxx)	Placebo (N=xxx)	Amifampridine (N=xxx)	Placebo (N=xxx)
Denominator Based on Subjects Who Completed Day 0 3TUG	xxx (xxx%)	xxx (xxx%)	xxx (xxx%)	xxx (xxx%)
Denominator Based on Subjects Who Completed Day 0 and Day 4 3TUG	xxx (xxx%)	xxx (xxx%)	xxx (xxx%)	xxx (xxx%)

Table Creation Date: (DD-MMM-YYYY) Source Program: xxxxxx.sas Source Listing: Data Listing 16

Table 33. Summary of Patient Most Bothersome Symptom Catalyst Pharmaceuticals, Inc. - LMS-003 FAS Population (N=xxx)

Treatment	Time Point ^a	Data Type ^b	Mean	Std Dev	n	Min	Max	Median	P-value ^c

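### Neither of the SAP's two exploratory 3TUG proportions cleanly gives known worsening events over subjects with a known outcome, and neither is named as the main one

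*SAP*

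**What the plan says.** SAP 4.2.2 defines the 3TUG event as a rise in average time of at least 20% from Day 0 to Day 4. It labels this a success, but it is a worsening. For a subject whose disease prevents completion on Day 4, "a success will be assigned to the subject by the site at the time of testing".

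The proportion is then calculated twice, each time with its own two-sided Fisher's exact test:

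- Method 1: "using all subjects in the analysis population with Day 0 data as the denominator, regardless of whether or not they completed" the Day 4 test. The Table 29 shell in SAP Appendix B words it as "Denominator Based on Subjects Who Completed Day 0 3TUG".
- Method 2: "using only those subjects in the analysis population who completed both the Day 0 and Day 4 assessments".

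The SAP does not say which result is the main one. Protocol 13.4 specifies Fisher's test for this proportion but no denominator.

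SAP 2.3 sets the general rule: "No missing value imputation will be used in this analysis. All analyses will be based on the observed data". Its one further provision is that observations taken at rescue are analysed with the Day 4 data. It makes no exception for 3TUG.

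**The concern.** The event is a bad outcome, so counting an untested subject as having no event gives that subject a good outcome. Method 1 does this to anyone in the denominator who has neither a post-baseline 3TUG nor an assigned event. Membership of the Full Analysis Set does not rule such subjects out. SAP 2.2 asks for one post-treatment efficacy assessment of any kind, and Protocol 11.3 places 3TUG last in the Day 4 sequence, so a subject can have SGI and QMG results but no 3TUG.

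Method 2 looks like the observed-data answer but has a gap of its own. A subject who could not complete Day 4 because of disability did not complete both tests. Read literally, the restriction removes that subject and the event the SAP has just assigned. These are the clearest cases of worsening.

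At stake is how an exploratory result is read: two p-values side by side, possibly on opposite sides of 0.05, with no rule for choosing between them.

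**Working it through.** The documents give no 3TUG event rate, 3TUG power or expected number of missing tests, so there is no plan figure to reproduce. The counting rules can be checked directly. Their effect can only be illustrated with assumed counts.

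**Inputs.** N = 13 per arm, from the total of 26 randomised 1:1 in SAP 1.3. Two-sided Fisher's exact test at 0.05, from SAP 4.2.2 and 2.1. Event counts and missing tests are assumed.

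**Rule.** In one arm let e be the events, m the subjects with no analysed post-baseline 3TUG and no assigned event, and d the site-assigned events (included in e).

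- Method 1: e/N
- Method 2, read literally: (e − d)/(N − m − d)
- Known outcomes: e/(N − m)
- Untested counted as worsened: (e + m)/N

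Method 1 falls short of the known-outcome proportion by e/(N − m) − e/N = e·m/[N(N − m)]. The gap grows with e, so a missing test matters more in the arm with more events. Between the two extreme assumptions each untested subject is worth 1/13 = 7.7 percentage points.

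**Example A: two placebo tests missing (e = 6, m = 2); amifampridine 1/13.**

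| Calculation | Placebo v amifampridine | p |
|---|---|---|
| Method 1 | 6/13 v 1/13 | 0.073 |
| Known outcomes | 6/11 v 1/13 | 0.023 |
| Untested counted as worsened | 8/13 v 1/13 | 0.011 |

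The gap for placebo is 6×2/(13×11) = 12/143 = 8.4 points (46.2% v 54.5%).

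For method 1, with 7 events in 26 subjects, the observed table and the more extreme one on the same side have probability (1716×13 + 1716)/657800 = 0.0365. With equal arms this doubles to 0.073. For known outcomes, with 7 events in 24, the tables no more likely than the observed one sum to (462×13 + 330 + 1716)/346104 = 0.023.

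**Method 2 in Example A.** If none of the six placebo events was site-assigned (d = 0), method 2 equals the known-outcome result. If two were (d = 2), it becomes (6 − 2)/(13 − 2 − 2) = 4/9 v 1/13. The p-value is (126×13 + 126 + 1287)/26334 = 0.116. Method 2 then moves further from the known-outcome result than method 1 does.

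**Example B: two amifampridine tests missing (e = 1, m = 2); placebo 7/13.**

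| Calculation | Amifampridine v placebo | p |
|---|---|---|
| Method 1 | 1/13 v 7/13 | 0.030 |
| Known outcomes | 1/11 v 7/13 | 0.034 |
| Untested counted as worsened | 3/13 v 7/13 | 0.226 |

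Here method 1 flatters the drug by only 1×2/143 = 1.4 points. The larger issue is that the result depends on two outcomes nobody saw, and the plan includes no analysis that would show it.

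**The case against.** The strongest reply is that the SAP already prints both proportions side by side in Table 29, so a reader can see whether missing tests matter, and method 1 has no priority merely because it is listed first. That is fair, and it limits the harm. It does not settle the matter: method 2 may drop the assigned events, and two tests with no stated order leave the choice open until the data are seen.

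The group affected should also be very small. There is one post-baseline visit, patients unable to ambulate are excluded, inability due to disease is scored as an event, and rescue observations count as Day 4. This stands.

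Three stronger readings are tempting and should not be drawn.

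- A reader might infer that subjects who stop early without rescue are left out, because the 3TUG paragraph lacks the early-time-point sentence given for QMG, SGI and the symptom question. The documents say otherwise. SAP 2.2 includes evaluations obtained at discontinuation, Protocol 13.4 allows an earlier result for every efficacy variable with a baseline, and Protocol 11.4 lists 3TUG at the early discontinuation visit. At most a cross-reference is missing.
- A reader might set method 1 against the result had everyone been tested. With 14 per arm, 7/14 v 1/14 gives p=0.033, while 5/14 v 1/14, with two worsened placebo subjects untested, gives p=0.16. But the known-outcome analysis of that case, 5/12 v 1/14, gives p=0.065. Much of the loss comes from the missing tests themselves, so the contrast overstates what the counting rule does.
- A reader might infer a bias toward the drug. The direction depends on which arm has the missing tests.

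**Conclusion.** The point holds as a defect in the counting rules. Method 1 scores untested, unassigned subjects as not worsened, against the statement that "No missing value imputation will be used in this analysis". Method 2, read literally, discards events that the SAP assigns. The disability assignment is also not reconciled with SAP 2.3. No method is designated as main.

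The consequence is minor. 3TUG is exploratory, the co-primary analyses are untouched, and few subjects should be affected. With arms this small, two missing tests can still put the result on the other side of 0.05, as Example A shows (0.073 v 0.023). That rests on assumed counts at 13 per arm and is not a forecast. The finding about method 2 rests on the literal sense of completing both assessments. If the sponsor meant to keep assigned events there, the SAP should say so.

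**What to change.** In SAP 4.2.2, make the main proportion worsening events over subjects with a known outcome. A known outcome is an observed post-treatment 3TUG (Day 4, rescue or early-discontinuation visit, in line with SAP 2.2, SAP 2.3 and Protocol 13.4) or a disability-assigned event. State the disability assignment as an exception in SAP 2.3. Keep the all-Day-0 denominator only as a sensitivity analysis, paired with one that counts untested subjects as worsened, so that both extremes are visible. Update the shells for Tables 29-32.

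The cost is SAP wording and table shells, with no new data collection. The main analysis has a slightly smaller N if tests are missing. It also takes those tests to be uninformative, which is why the paired sensitivity analyses are needed.
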